Effect of Transcranial Direct Current Stimulation on the Voice

Document date: 07/15/2024

Study protocol

The present study was approved by the Research Ethics Committee of the institution where the research was conducted (n. 5.758.856). All included volunteers signed the written informed consent prior to the experiment.

Vocally healthy individuals were recruited from the university community. We included volunteers of both sexes, aged 18 to 45 years, who scored up to 16 points on the Vocal Symptoms Scale (VSS), Brazilian version. The Brazilian Dysphonia Screening Tool (Br-DST) was also applied, and those who answered "yes" to both questions would be excluded.

Through a crossover study design, the volunteers underwent four experimental sessions separated by 7 days-minimum washout period to prevent cumulative effects of stimulations. In each session, a single target area was stimulated: (i) left laryngeal M1, (ii) left S1 of the larynx, (iii) left DLPFC, and (iv) cerebellum. The order of sessions was randomized in order counterbalanced by an external researcher to ensure blinding of both volunteer and therapist during vocal assessment. The allocation of sessions was securely concealed within opaque, sealed envelopes that were accessible only to the researcher responsible for tDCS.

The electrode setup during the tDCS sessions was as follows: (i) For left laryngeal M1, the anode was positioned over C5 (international 10-20 EEG system) and the cathode over the contralateral supraorbital region; (ii) For the left S1 of the larynx, the anode was positioned 3 cm posterior to C5 and the cathode over the contralateral supraorbital region; (iii) For left DLPFC, the anode was positioned over F3 and the cathode over the contralateral supraorbital region; (iv) For the cerebellum, the anode was placed over inion and the cathode over the right deltoid muscle. During the tDCS session, volunteers were instructed to sit in a chair and find a comfortable position. tDCS was delivered by an electrical stimulator (Neuroconn, Germany) through a pair of saline-soaked sponge electrodes (35 cm²) with a current intensity of 2mA for 20 minutes.

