Before and after each session, volunteers were systematically evaluated for vocal acoustic parameters and laryngeal diadochokinesis. The vocal assessment analysis was performed immediately before and after tDCS using the Voxmetria and Vocalgrama software from CTS Informatics. Voice recordings were conducted using an HP Notebook Acer Aspire 5 PC with a Karsect HT-2° headset microphone and Andrea PureAudio™ USB-AS sound signal amplifier equipment. The microphone was positioned four centimeters away from the mouth at a

45-degree angle, with the participant seated and hands resting on their legs, forming a 90-degree angle.

The following tasks were requested: (i) Evaluation of vocal quality through sustained vowel / ϵ / for 5 seconds at weak intensity (below 70dB), habitual intensity (between 70 and 80dB), and strong intensity (above 80dB), controlled with a decibel meter. (ii) Cepstral analysis with sustained vowel / ϵ / for 5 seconds and the phrase "olha lá o avião azul" at weak, habitual, and strong intensities (as defined above), controlled with a decibel meter. (iii) Diadochokinesis assessment with the task of emitting vowels /a/ and /i/ separately, with rapid and interrupted repetitions of each vowel as fast as possible for eight seconds. (iv) Pitch range assessment through ascending and descending glissandos up to the maximum vocal extension in weak and strong emissions. (v) Assessment of reported vocal effort with sustained vocal effort emission. For phase 1, participants were asked to reproduce a note using a virtual keyboard (3 tones below their maximum glissando frequency) and then maintain that tone while counting from 21 to 30. Immediately afterwards, the participants answered the Adapted Borg CR10 for Vocal Effort Ratings (BR)¹⁷. Like the original protocol, the Adapted Borg CR10 for Vocal Effort Ratings (BR) maintained a scale from 0 to 10, where 0 means "no vocal effort at all", and 10 "maximum vocal effort".

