For Vocal range profile, the participants were instructed to produce ascending (from low to high) and descending (from high to low) glissandos of the vowel / ϵ / as weak as possible and as strong as possible intensities. As the participant produced the vowel / ϵ / in ascending and descending glissando, the graph was marked with dots that corresponded to the frequency (abscissa) and intensity (ordinate) of the vocal productions. The participants were asked to emit the loudest possible tone during the vocal productions of glissando. The assessment of diadochokinesis was performed by counting peaks per second in the spectrogram, excluding the initial and final two seconds for analysis. For the analysis of acoustic parameters, the recording of the vowel / ϵ / was edited by discarding the first and last minutes of emission (as these segments showed greater instability), considering approximately three seconds of emission for analysis. The assessment of diadochokinesis was performed by counting peaks per second in the spectrogram, excluding the initial and final two seconds for analysis.

Statistical Analysis

The sample size was determined using the Sample Size Calculators tool designed by David Schoenfeld with the support of the Massachusetts General Hospital - Mallinckrodt General Clinical Research Center (http://hedwig.mgh.harvard.edu/sample_size/js/js_crossover_quant.html).

The calculation was carried out with 12 volunteers, considering the minimum detectable difference ($MDD: 1.96StandardError\sqrt{2}$) and the standard deviation of the primary outcome measures. A statistical power (β) of 80% and a significance level (α) of 5% were considered.

For data analysis, normality was tested using the Shapiro-Wilk test. To compare pre and post stimulation results, the Student's t-test was applied for parametric data and the Wilcoxon signed-rank test for non-parametric data. To compare the effects of tDCS across different time points, a Friedman ANOVA for repeated measures was conducted, followed by pairwise post hoc comparisons with a significance level of 5% ($p < 0.05$). All analyses were performed in SPSS software (version 26.0, SPSS Inc, Chicago, USA).

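### The only test that could compare the four stimulation sites does not name site as its factor, define what is ranked, or adjust the pairwise comparisons

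*Combined protocol and SAP*

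**What the plan says.** Under Study protocol, the design is a four-session crossover. "In each session, a single target area was stimulated", with four areas in all, and "The order of sessions was randomized in order counterbalanced by an external researcher". Site is therefore the randomised factor. Measurements are taken twice per session: "Before and after each session, volunteers were systematically evaluated for vocal acoustic parameters and laryngeal diadochokinesis". Each volunteer thus supplies eight values per outcome.

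Under Statistical Analysis, two kinds of comparison are planned. "To compare pre and post stimulation results", a t-test or a Wilcoxon signed-rank test is used. The second comparison is the Friedman test: "To compare the effects of tDCS across different time points, a Friedman ANOVA for repeated measures was conducted". The same sentence then adds the pairwise step: "followed by pairwise post hoc comparisons with a significance level of 5" per cent. The section does not mention target area. It does not say whether post values, changes or raw pre and post values are ranked, and it names no pairwise test, no family of comparisons and no multiplicity adjustment.

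**The concern.** The pre/post tests do not compare sites, so the Friedman test has to carry the question the crossover was built to answer. Its stated factor is time. A volunteer has two time points within a session, four sessions in calendar order, and eight measurements overall, and none of these is the site factor. A result significant over sessions may show drift across visits. A result significant over all eight cells may show a before/after change shared by every site, such as practice or fatigue from repeating the voice tasks. Reported as an answer to the site question, either would mislead.

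The post hoc step has its own gap. A preceding omnibus test limits false pairwise findings when no site differs. Once one site does differ, the omnibus test is usually passed if the difference is large, and the remaining equal sites are then compared without protection.

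**Working it through.** **1. Readings of the sentence**

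| Reading | Columns ranked | Pairs | Isolates site? |
|---|---|---|---|
| Sessions in calendar order | 4 | C(4,2) = 6 | No |
| All pre and post cells | 8 | C(8,2) = 28 (6 post–post, 6 pre–pre, 16 pre–post) | Not as an omnibus test |
| Post values by site | 4 | 6 | Yes |
| Post-minus-pre changes by site | 4 | 6 | Yes |

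A two-column test of pre against post also fits the words. It would repeat the t-test/Wilcoxon comparison and leave a single pair, so no figures are rested on it.

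**2. Inputs**

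From the documents: four sites, four sessions, two measurements per session, α = 5%, and "The calculation was carried out with 12 volunteers". Whether 12 is the planned number is unclear, but it is the only one given. No SD is stated.

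Assumed: normal data; SDs of 1.0 between volunteers, 0.5 between sessions and 0.4 for measurement error; a Williams-balanced order. Shifts and trends are in the same units. The SD of a change is √(2 × 0.4²) = 0.57, so a shift of 0.2–0.5 is 0.35–0.88 SD of change. There were 10,000 simulated trials per scenario, giving a Monte Carlo SE of at most √(0.25/10,000) = 0.5 points.

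**3. Test**

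Q = 12/[nk(k+1)] × ΣR_j² − 3n(k+1), referred to χ² on k−1 df, with n = 12 and k = 4 or 8.

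**4. Omnibus rejection with no site difference**

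| Reading | Assumed effect | Rejection |
|---|---|---|
| Sessions 1–4, post values | trend 0 / 0.1 / 0.2 / 0.3 / 0.4 per session | 5 / 11 / 35 / 70 / 93% |
| Sessions 1–4, changes | level trend 0 to 0.4 | 4–5% |
| Eight cells | common shift 0 / 0.2 / 0.3 / 0.4 / 0.5 | 6 / 14 / 31 / 59 / 85% |
| Post values by site | trend 0 to 0.4 | falls from 4.7% to 0.7% |
| Changes by site | any of these shifts or trends | 4–5% |

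A second set of assumptions (SD of change 1, between-volunteer SD 1.5, session SD 0.5, n = 12) shows the same pattern. Eight cells reject in 11, 42 and 91% of trials for common changes of 0.25, 0.5 and 0.8. Sessions on post values reject in 30% for a trend of 0.25 per session. Changes by site reject in 4.3–5.0%.

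**5. Pairwise step**

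Changes are ranked by site, and six exact signed-rank tests are read only after a significant Friedman test. One site is shifted and the other three are equal.

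| True shift of one site | False difference among the other three: unadjusted | with Holm | Power per true pair: unadjusted | with Holm |
|---|---|---|---|---|
| 0.3 | 5% | 2% | 9% | 4% |
| 0.5 | 8% | 2% | 31% | 18% |
| 0.7 | 10% | 3% | 63% | 44% |
| 1.0 | 11% | 4% | 94% | 83% |
| 1.4 | 11% | 4% | 100% | 99% |

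With no site difference at all, the gated unadjusted rate is 4%. Under the second set of assumptions, with one site differing by 1–2 SD of change, it is 8.6–11.1% at n = 12 and 12.0–13.1% at n = 24.

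**The case against.** The strongest reply is that this is loose English. Pre against post already has its own test, so a test of the effects of tDCS that is followed by several pairwise comparisons most naturally means the four conditions, and effects most naturally means changes. On that reading the omnibus test holds its level. This stands as a possibility, but the documents do not settle it.

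A reader might infer that the plan has an inflated type I error. The documents do not support that. Under the literal readings the test correctly detects a real trend or a real common change. The harm comes only if that result is reported as a site difference, and nothing in the text does so. With neither effect present, rejection is near 5%. Ranking changes over sessions also stays at 4–5% under a trend in level.

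A reader might also infer that the site question has no test at all. That goes too far: the eight-cell reading includes six post–post site pairs. What is missing is a dedicated omnibus test of site.

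Finally, one might argue that Friedman should give way to a mixed model. That is a trade-off, not a correction. The plan foresees non-normal outcomes ("normality was tested using the Shapiro-Wilk test"), and in simulations with untransformed lognormal errors the model had less power than the better of the two by-site Friedman tests, by 0.5 to 9 points.

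On the pairwise step, the order of the wording suggests that the omnibus test acts as a gate, and the gate does protect when all sites are equal. The excess is modest and appears only when one site truly differs.

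**Conclusion.** The concern holds as a defect of specification that should be fixed. Followed as written, the test does not isolate a site effect. If site was in fact the ranked factor, the remaining omnibus defect is that the text does not say so. The rejection rates of 11–93% and 14–85% show what the literal readings could pick up. They are not error rates of the trial: they require a session trend or a common pre/post change of the assumed size, and they rest on assumed SDs and on 12 volunteers. The absence of an adjustment is a separate, smaller gap that remains under every by-site reading: about 5–11% against 2–4% with Holm, depending on how far one site differs. Confidence is high on the wording and medium on the magnitudes.

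**What to change.** Replace the Friedman sentence with:

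> For each outcome the four target areas are compared by Friedman's test on the four post-minus-pre changes, with target area (4 levels) as the factor, followed by six pairwise Wilcoxon signed-rank tests, Holm-adjusted.

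Changes are suggested because they are unaffected by a trend in level, whereas post values by site become conservative. With one site shifted by 0.7, power is about 59% for post values and 71% for changes, and 26% and 71% with a trend of 0.4. This ordering depends on the SDs. Within-volunteer variance is 0.5² + 0.4² = 0.41 for a post value and 2 × 0.4² = 0.32 for a change, so changes lose their advantage if session SD falls below error SD and there is no trend.

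No new data are needed. The cost is power for individual pairs, from 63% to 44% at a shift of 0.7 and from 94% to 83% at 1.0, and little beyond that. The omnibus test is not affected.

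The text is in the past tense. If results have been seen, state what was actually ranked, which is not a post hoc change, and label any change of response or method as post hoc. A mixed model with site and period may be added as an optional sensitivity analysis for outcomes that are approximately normal or log-transformed.
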